**Table 5: Target Visit/Days for MAD**

Dose (Visit)	Expected date EXPDATE (Dose n-1 date + expected number of days)	Target Dose Visit Date
Dose 1 (Day 1)	Day 1	Dose 1 date
Dose 2 (Day 3)	Dose 1 date + 2 days (i.e. 3-1), time 00:00	
 
• If any dose within expected date +/-1 days then = this dose date,
 
• else = expected date (i.e. = Dose 1 date + 2 days)
 

Day 4	Day 3 Target date+1 day	Day 3 Target date+1 day
Dose 3 (Day 5)	Day 3 Target date + 2 days (5-3), time 00:00	
 
• If any dose within expected date +/-1 days then = this dose date,
 
• else = expected date (i.e. Day 3 Target Date + 2 days)
 

Dose 4 (Day 8)	Day 5 Target date + 3 days (8-5), time 00:00	"
Dose 5 (Day 10)	Day 8 Target date + 2 days, time 00:00	"
Dose 6 (Day 12)	Day 10 Target date + 2 days, time 00:00	"
Dose 7 (Day 15)	Day 12 Target date + 3 days, time 00:00	"
Dose 8 (Day 17)	Day 15 Target date + 2 days, time 00:00	"
Dose 9 (Day 19)	Day 17 Target date + 2 days, time 00:00	"
Dose 10 (Day 22)	Day 19 Target date + 3 days, time 00:00	"
Dose 11 (Day 24)	Day 22 Target date + 2 days, time 00:00	"
Dose 12 (Day 26)	Day 24 Target date + 2 days, time 00:00	"
Day 33	Day 26 Target date + 7 days	Day 26 Target date + 7
Day 54	Day 26 Target date + 28 days	Day 26 Target date + 28

For time points with time precision relative to dose (i.e. "Dose time+ XX min"), the time is computed with respect to the end time of dosing (end of inhalation).

4.2.7.2. Spirometry

**Table 6: Time Point for Spirometry SAD**

Time point	Target	Interval for Analysis
Baseline	Pre-dose Day 1	Most recent value prior to first dose
Day 1 10 min Post-dose	Day 1 dose end time+10 min	]Day 1 dose end time, Day 1 dose end time+20 min]
Day 1 30 min Post-dose	Day 1 dose end time+30 min	]Day 1 dose end time+20min, Day 1 dose end time+45 min]
Day 1 60 min Post-dose	Day 1 dose end time+60 min	]Day 1 dose end time+45min, Day 1 dose end time+90 min]
Day 1 2 hr Post-dose	Day 1 dose end time+2 hours	]Day 1 dose end time+90min, Day 1 dose end time+3h]
Day 1 4 hr Post-dose	Day 1 dose end time+4 hours	]Day 1 dose end time+3h, Day 1 dose end time+6h]
Day 1 8 hr Post-dose	Day 1 dose end time+8 hours	]Day 1 dose end time+6h, Day 2[
Day 2	Day 2	[Day 2, Day 4[
Day 4	Day 4	[Day 4, Day 7[
Day 8	Day 8	[Day 7, End of Study]

**Table 7: Time point for Spirometry MAD**

Time point	Target Date/Time	Interval for Analysis
Baseline	Day 1 dose start time	Most recent value prior to first dose
Day 1 10 min Post-dose	Day 1 dose end time+10 min	]Day 1 dose end time, Day 1 dose end time +20min]
Day 1 30 min Post-dose	Day 1 dose end time+30 min	]Day 1 dose end time+20min, Day 1 dose end time +45min]
Day 1 60 min Post-dose	Day 1 dose end time+60 min	]Day 1 dose end time+45min, Day 1 dose end time +90min]
Day 1 2 hr Post-dose	Day 1 dose end time+2 hours	]Day 1 dose end time+90min, Day 1 dose end time +3h]
Day 1 4 hr Post-dose	Day 1 dose end time+4 hours	]Day 1 dose end time+3h, Day 1 dose end time +6h]
Day 1 8 hr Post-dose	Day 1 dose end time+8 hours	]Day 1 Dose end time+6h, Day 2[
Day 3 Pre-dose	Day 3 dose start time	[Day 2, Day 3 dose start time[
Day 3 20 min Post-dose	Day 3 dose end time +20 min	]Day 3 dose end time, Day 3 dose end time +40min]
Day 3 60 min Post-dose	Day 3 dose end time +60 min	]Day 3 dose end time+40min, Day 3 dose end time +2h]
Day 3 4 hr Post-dose	Day 3 dose end time+4 hours	]Day 3 dose end time+2h, Day 4[
Day 4	Day 4	]Day 3, Day 5[
Day 5 Pre-dose	Day 5 dose start time	[Day 5, Day 5 dose start time[
Day 5 20 min Post-dose	Day 5 dose end time +20 min	]Day 5 dose end time, Day 5 dose end time +40min]
Day 5 60 min Post-dose	Day 5 dose end time +60 min	]Day 5 dose end time+40min, Day 6]
Day 8 Pre-dose	Day 8 dose end time	[Day 7, Day 8 dose end time[
Day 8 20 min Post-dose	Day 8 dose end time +20 min	]Day 8 dose end time, Day 8 dose end time +40min]
Day 8 60 min Post-dose	Day 8 dose end time +60 min	]Day 8 dose end time+40min, Day 10]
Day 15 Pre-dose	Day 15 dose start time	]Day 10, Day 15 dose start time[
Day 15 20 min Post-dose	Day 15 dose end time +20 min	]Day 15 dose end time, Day 15 dose end time +40min]
Day 15 60 min Post-dose	Day 15 dose end time +60 min	]Day 15 dose end time+40min, Day 17]
Day 22 Pre-dose	Day 22 dose start time	]Day 17, Day 22 dose start time[
Day 22 20 min Post-dose	Day 22 dose end time +20 min	]Day 22 dose end time, Day 22 dose end time +40min]
Day 22 60 min Post-dose	Day 22 dose end time +60 min	]Day 22 dose end time+40min, Day 24 ]
Day 26 Pre-dose	Day 26 dose start time	]Day 24, Day 26 dose start time[
Day 26 20 min Post-dose	Day 26 dose end time +20 min	]Day 26 dose end time, Day 26 dose end time +40min]
Day 26 60 min Post-dose	Day 26 dose end time +60 min	]Day 26 dose end time+40min, Day 26 +3 days ]

Day 33	Day 33	[Day 26+4 ; Day 33+7]
Day 54	Day 54	[Day 33+8 ; End of Study]

#### 4.2.7.3. Laboratory Tests

**Table 8: Time points for Hematology and Chemistry SAD**

Time point	Target	Interval for Analysis
Baseline	Day 1 dose start time	Most recent value prior to first dose
Day 1 30 min Post-dose	Day 1 dose end time+30 min	]Day 1 dose end time, Day 1 dose end time +45 min]
Day 1 60 min Post-dose	Day 1 dose end time+60 min	]Day 1 dose end time+45min, Day 1 dose end time+90min]
Day 1 2 hr Post-dose	Day 1 dose end time+2 hours	]Day 1 dose end time+90min,Day 1 dose end time+3h]
Day 1 4 hr Post-dose	Day 1 dose end time+4 hours	]Day 1 dose end time+3h, Day 1 dose end time+6h]
Day 1 8 hr Post-dose	Day 1 dose end time+8 hours	]Day 1 dose end time+6h,Day 1 dose end time+10h]
Day 1 12 hr Post-dose	Day 1 dose end time+12 hours	]Day 1 dose end time+10h, Day 2[
Day 2	Day 2	[Day 2, Day 3[
Day 3	Day 3	[Day 3, Day 4[
Day 4	Day 4	[Day 4, Day 7[
Day 8	Day 8	[Day 7, End of study]

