4.2 Study Design

The study is a multicenter, randomized, double-blind, and placebo-controlled Phase 1b SAD and MAD design. The subject, investigator, and site personnel (except pharmacist) will be blinded to treatment, while the sponsor will be unblinded. Sponsor personnel will be unblinded to subject

treatments in order to permit real-time interpretation of the safety, pharmacokinetic, and pharmacodynamic data. The site monitor will remain blinded to individual subject treatment allocation until all monitoring of study data has been completed. To minimize the potential for bias, individual subject treatment randomization information will not be released to the investigator or blinded study site personnel until the study database has been locked.

Eligible subjects with homozygous $\Delta F508$ CF will be randomized at a 3:1 ratio to receive either QR-010 or placebo via oral inhalation (nebulization). This study will be conducted in North America and select European countries.

[figure not shown]
The study includes 2 stages. The first stage is a single ascending dose-escalation (SAD) design to determine safety and tolerability of a single dose of QR-010. The second stage is a multiple ascending dose escalation (MAD) design to further assess the safety, tolerability, and exploratory efficacy of 12 doses of QR-010 over 4 weeks. All doses will be administered in a clinical setting.

For the SAD cohorts, subjects will receive the dose in an inpatient observation unit and be observed for a total 4 days, and will be discharged on Day 4. Subjects will return for PK and safety follow-up as an outpatient on Day 8 (End of Study Visit).

For the MAD cohorts, subjects will receive doses 1 through 12 in a clinic while under observation. On Day 1 and Day 3 subjects will be observed until 12 hours post dose. Following the last dose (dose 12), subjects will return twice for PK sampling, and will be evaluated 7 and 28 days after the last visit for this additional safety monitoring and sampling for PK.

A schematic of the study design is presented in Figure 3.

Figure 3: PQ-010-001 Study Schematic

Single Ascending Dose Escalation Cohorts: The first two subjects of each cohort may be dosed on the same day, at least 4 hours apart. If no significant AEs occur, the remainder of the cohort may be dosed at least 24 hours later, with at least 1 hour between subjects.

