#### 4.2.7. Visit Windows

##### 4.2.7.1. General Rules

##### Definition of target visit dates for SAD:

Day 1 is defined as the date of first (and unique) dose. Day 2,3,4,8 are defined relatively to Day 1 (Ex: Day 4=Day 1+3).

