#### 4.2.7.5. Vital Signs and Weight

**Table 18: Time points for Vital Signs SAD**

Time point	Target	Interval for Analysis
Baseline	Day 1 dose start time	Most recent value prior to first dose
Day 1 1min Post-dose	Day 1 dose end time+1min	]Day 1 dose end time, Day 1 dose end time+5min]
Day 1 10 min Post-dose	Day 1 dose end time+10min	]Day 1 dose end time+5min, Day 1 dose end time+20min]
Day 1 30min Post-dose	Day 1 dose end time+30min	]Day 1 dose end time+20min, Day 1 dose end time+45min]
Day 1 60min Post-dose	Day 1 dose end time+60min	]Day 1 dose end time+45min, Day 1 dose end time+90min]
Day 1 2hrs Post-dose	Day 1 dose end time+2h	]Day 1 dose end time+90min, Day 1 dose end time+3h]
Day 1 4hrs Post-dose	Day 1 dose end time+4h	]Day 1 dose end time+3h, Day 1 dose end time+8h]
Day 1 12hrs Post-dose	Day 1 dose end time+12h	]Day 1 dose end time+8h, Day 2[
Day 2	Day 2	[Day 2, Day 3[
Day 3	Day 3	[Day 3, Day 4[
Day 4	Day 4	[Day 4, Day 7[
Day 8	Day 8	[Day 7, End of Study]

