**Table 20: Time points for Vital Signs MAD**

Time point	Target	Interval for Analysis
Baseline	Day 1 dose start time	Most recent value prior to first dose
Day 1 1min Post-dose	Day 1 dose end time+1min	]Day 1 dose end time, Day 1 dose end time+5min]
Day 1 10 min Post-dose	Day 1 dose end time+10min	]Day 1 dose end time+5min, Day 1 dose end time+20min]
Day 1 30min Post-dose	Day 1 dose end time+30min	]Day 1 dose end time+20min, Day 1 dose end time+45min]
Day 1 60min Post-dose	Day 1 dose end time+60min	]Day 1 dose end time+45min, Day 1 dose end time+90min]
Day 1 2hrs Post-dose	Day 1 dose end time+2h	]Day 1 dose end time+90min, Day 1 dose end time+3h]
Day 1 4hrs Post-dose	Day 1 dose end time+4h	]Day 1 dose end time+3h, Day 1 dose end time+8h]
Day 1 12hrs Post-dose	Day 1 dose end time+12h	]Day 1 dose end time+8h, Day 3[
Day 3 Pre-dose	Day 3 dose start time	[Day 3, Day 3 dose start time[
Day 3 1min Post-dose	Day 3 dose end time+1min	]Day 3 dose end time, Day 3 dose end time+5min]
Day 3 10 min Post-dose	Day 3 dose end time+10min	]Day 3 dose end time+5min, Day 3 dose end time+20min]
Day 3 30min Post-dose	Day 3 dose end time+30min	]Day 3 dose end time+20min, Day 3 dose end time+45min]
Day 3 60min Post-dose	Day 3 dose end time+60min	]Day 3 dose end time+45min, Day 3 dose end time+90min]
Day 3 2hrs Post-dose	Day 3 dose end time+2h	]Day 3 dose end time+90min, Day 3 dose end time+3h]
Day 3 4hrs Post-dose	Day 3 dose end time+4h	]Day 3 dose end time+3h, Day 3 dose end time+8h]
Day 3 12hrs Post-dose	Day 3 dose end time+12h	]Day 3 dose end time+8h, Day 4[
Day 4	Day 4	[Day 4, Day 5[
Day 5 Pre-dose	Day 5 dose start time	[Day 5, Day 5 dose start time[
Day 5 1min Post-dose	Day 5 dose end time+1min	]Day 5 dose end time, Day 5 dose end time+5min]
Day 5 10 min Post-dose	Day 5 dose end time+10min	]Day 5 dose end time+5min, Day 5 dose end time+20min]
Day 5 30min Post-dose	Day 5 dose end time+30min	]Day 5 dose end time+20min, Day 5 dose end time+45min]
Day 5 60min Post-dose	Day 5 dose end time+60min	]Day 5 dose end time+45min, Day 5 dose end time+90min]
Day 5 2hrs Post-dose	Day 5 dose end time+2h	]Day 5 dose end time+90min, Day 7[
Day 8 Pre-dose	Day 8 dose start time	[Day 7, Day 8 dose start time[
Day 8 1min Post-dose	Day 8 dose end time+1min	]Day 8 dose end time, Day 8 dose end time+5min]
Day 8 10 min Post-dose	Day 8 dose end time+10min	]Day 8 dose end time+5min, Day 8 dose end time+20min]

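### SAD laboratory and vital-sign windows (SAP Tables 8 and 18) end the 12 h window at midnight, so a dose that ends at or after noon sends the 12 h reading to Day 2

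*SAP*

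**What the plan says.** SAP 4.2.7.1 sets the SAD calendar: "Day 1 is defined as the date of first (and unique) dose", and "Day 2,3,4,8 are defined relatively to Day 1 (Ex: Day 4=Day 1+3". Both are dates without a clock time. Hour offsets work differently: "the time is computed with respect to the end time of dosing (end of inhalation".

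The last Day 1 windows combine the two systems:

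- Table 8 (SAD haematology and chemistry), 12 h: "Day 1 dose end time+10h, Day 2", open at both ends. The Day 2 window starts at Day 2, inclusive, and runs to Day 3.
- Table 18 (SAD vital signs), 12 h: "Day 1 dose end time+8h, Day 2", with the same Day 2 window. SAP 4.10.3 summarises oximetry with the vital signs.
- Table 6 (SAD spirometry), 8 h: "Day 1 dose end time+6h, Day 2". Table 7 (MAD spirometry) has the same Day 2 cut for its Day 1 8 h row.
- Table 20 (MAD vital signs), Day 3 12 h row: "Day 3 dose end time+8h, Day 4".

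Protocol 7.3.2 schedules SAD laboratory tests, vital signs and oximetry at 12 h after dosing. Protocol 7.3.3 places the Day 2 laboratory sample at 24 h, but gives no hour for Day 2 vital signs, oximetry or spirometry. No clock time for dosing is stated. Protocol 4.2 allows a stagger within a day: "The first two subjects of each cohort may be dosed on the same day, at least 4 hours apart".

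**The concern.** A window whose start is counted from the end of inhalation and whose end is a calendar midnight gets shorter the later in the day a subject is dosed. After an afternoon dose, the scheduled 12 h reading falls past midnight and into the Day 2 window, which also holds the scheduled Day 2 reading.

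The SAP says how to handle several values for sweat chloride (average those of the same day) and for MAD glucose (first of the day). It has no such rule for other laboratory tests or for vital signs. Depending on the programmer, the 12 h value could be averaged with the Day 2 value, replace it or be dropped. In cohorts of six active subjects, a few misplaced values can change a cell, and which subjects are misplaced depends only on the clock time of dosing.

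**Working it through.** **Inputs.** Window definitions from SAP Tables 6, 8 and 18; Day 2 = dose date + 1 (SAP 4.2.7.1), so it begins at 00:00; offsets from the end of inhalation; scheduled readings from Protocol 7.3.2 and 7.3.3. Readings are taken at their nominal times. The plan states no figure of its own to reproduce.

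**Step 1: when a reading crosses midnight.** Let *e* be the clock time at which dosing ends.

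- 12 h reading: in Day 2 if *e* + 12 h ≥ 24:00, so *e* ≥ 12:00. Noon itself counts because the Day 2 window includes its lower limit.
- 8 h reading: in Day 2 if *e* + 8 h ≥ 24:00, so *e* ≥ 16:00.
- Length of the Table 8 12 h window: 24:00 − (*e* + 10 h) = 14:00 − *e*.

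| Dose end | 12 h sample due | Table 8 12 h window | 12 h sample assigned to | 8 h laboratory sample assigned to |
|---|---|---|---|---|
| 08:00 | 20:00 | 6 h long | 12 h | 8 h |
| 11:45 | 23:45 | 2.25 h long | 12 h | 8 h |
| 12:00 | 00:00, Day 2 | 2 h long | Day 2 | 8 h |
| 14:00 | 02:00, Day 2 | empty | Day 2 | 8 h |
| 16:00 | 04:00, Day 2 | empty | Day 2 | 8 h and Day 2 |

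Table 18 gives the same noon threshold for vital signs and oximetry. In every row the 24 h laboratory sample is in Day 2, so from noon onward Day 2 holds two scheduled samples.

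**Step 2: how many subjects.** This is an assumption, because no dosing times are given. Take 20 minutes for nebulisation (Protocol 6.2.1 gives about this as an upper figure), so a subject is affected if dosing starts at 11:40 or later. Dose the first pair 4 h apart on one day. Dose the other six either 1 h apart on one day (the minimum in Protocol 4.2) or 4 h apart at two per day (Protocol 4.3 states a 4 h minimum between subjects of a cohort). Those two spacing rules need to be reconciled; both are counted here.

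| First start | Pair | Other six, 1 h | Total of 8 | Other six, 4 h | Total of 8 |
|---|---|---|---|---|---|
| 07:00 | 0 | 1 | 1 | 0 | 0 |
| 07:30 | 0 | 1 | 1 | 0 | 0 |
| 08:00 | 1 | 2 | 3 | 3 | 4 |
| 09:00 | 1 | 3 | 4 | 3 | 4 |

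The range is 0 to 4 of 8 per cohort, or 4 × 0 = 0 to 4 × 4 = 16 of 32 SAD subjects. The latest dose end in any of these schedules is 14:20 (09:00 + 5 h + 20 min), so none reaches the 16:00 threshold for the 8 h readings.

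**Step 3: MAD windows.** The Day 1 12 h windows run to the end of the Day 3 dose (Table 9) or to Day 3 (Table 20), so the scheduled 12 h reading stays in its window at every dose-end time. In Table 20 only the Day 3 12 h row is in question. If Day 4 starts at midnight, a Day 3 dose ending at or after 12:00 moves that reading to Day 4. If Day 4 carries the clock time of the Day 3 dose, it does not move.

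**The case against.** **Afternoon dosing is permitted but not shown to be usual.** Protocol 4.2 says the first two subjects may share a day, not that they must. The protocol plans about 20 sites (5.2) or 27 (synopsis), so 32 SAD subjects average fewer than two per site, and subjects at different sites can be dosed on different days. This stands: a reader might infer that 12 to 16 of 32 subjects are affected, but that needs first starts at 08:00 or 09:00, and a 07:00 or 07:30 start gives 0 or 1 of 8.

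**Little is lost.** SAP 4.10.2.1 lists all laboratory data, uses all post-baseline values in the shift tables, and counts out-of-range values overall as well as by time point. Vital signs are listed by subject. The liver-test and hypoxia events of interest carry no visit window. Protocol 4.1.2 defines the secondary safety endpoint as change to end of treatment, or abnormalities seen on frequent monitoring; neither rests on the 12 h cell. This also stands. It would be wrong to infer that the secondary safety endpoint or the dose-escalation decisions are compromised.

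**Spirometry.** A reader might infer that 8 h readings contaminate the Day 2 level of the SAD mixed model (SAP 4.8.1.1), which leaves out Day 1 post-dose values. That needs dosing to end at or after 16:00, and the analysis is exploratory.

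**MAD vital signs.** A reader might infer that Table 20 shares the fault. The calendar-date rule is stated for SAD. For MAD subjects with all 12 doses, SAP 4.2.7.1 uses the dose dates and times as targets, and Table 5 puts Day 4 one day after the Day 3 target. The text is ambiguous, so the fault is not established there.

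**What the objection does not remove.** Tables 8 and 18 give the wrong assignment on their stated definitions whenever dosing ends at or after noon. Reading Day 2 as dose time + 24 h would not help either: a 24 h sample drawn slightly early would then fall in the 12 h window.

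**Conclusion.** The point holds for Tables 8 and 18. When dosing ends at or after 12:00, the scheduled 12 h laboratory tests, vital signs and oximetry are assigned to Day 2 with the scheduled Day 2 reading, the 12 h cell is empty, and nothing selects between the two values. In Table 8 the 12 h window is empty for dose ends from 14:00, and from 16:00 the 8 h sample fits two windows.

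The number affected is unknown: 0 to 16 of 32 SAD subjects under the assumed queues, and none if all dosing ends before noon. The noon threshold assumes collection at the nominal time; a sample taken early or late shifts it by the same amount. The damage is limited to by-time-point descriptive summaries. Tables 6 and 7 are exposed only if dosing ends at or after 16:00, and Table 20 only if its Day 4 boundary means midnight. The correction is cheap and worth making before the tables are produced.

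**What to change.** - **Table 8:** close the 12 h window and open Day 2 at Day 1 dose end + 18 h, the midpoint (12 + 24) / 2 of the two scheduled samples. This separates them at every dosing time and removes the 8 h overlap.
- **Table 18:** do not use a fixed + 18 h cut, because Day 2 vital signs and oximetry have no stated hour. After a 14:20 dose end, + 18 h is 08:20 on Day 2, and an 08:00 Day 2 reading would be labelled 12 h. Assign scheduled readings by their recorded nominal time point, and use the window only for unscheduled readings. If two values fall in one window, take the one closest to target.
- **Tables 6 and 7:** use the same nominal-time assignment for the 8 h spirometry. A fixed + 16 h cut would have the same drawback: a 16:20 dose end again gives 08:20 on Day 2.
- **Table 20, Day 3 12 h row:** state whether the Day 4 boundary is midnight or carries the dose clock time. Only midnight needs changing.

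The cost is SAP wording in a few tables and a small programming change, with no new data. Protocol 7.1 already requires actual times on the CRF. It is assumed that the database also carries the nominal time-point label; this should be confirmed.

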**Table 9: Time points for Hematology and Chemistry MAD**

Time point	Target	Interval for Analysis
Baseline	Day 1 dose start time	Most recent value prior to first dose
Day 1 30 min Post-dose	Day 1 dose end time+30 min	]Day 1 dose end time, Day 1 dose end time +45 min]
Day 1 60 min Post-dose	Day 1 dose end time+60 min	]Day 1 dose end time+45min, Day 1 dose end time+90min]
Day 1 2h Post-dose	Day 1 dose end time+2 hours	]Day 1 dose end time+90min,Day 1 dose end time+3h]
Day 1 4h Post-dose	Day 1 dose end time+4 hours	]Day 1 dose end time+3h, Day 1 dose end time+6h]
Day 1 8h Post-dose	Day 1 dose end time+8 hours	]Day 1 dose end time+6h, Day 1 dose end time+10h]
Day 1 12h Post-dose	Day 1 dose end time+12 hours	]Day 1 dose end time+10h, Day 3 dose end time]
Day 3 60min Post-dose	Day 3 dose end time+60min	]Day 3 dose end time, Day 3 dose end time+180min]
Day 3 4h Post-dose	Day 3 dose end time+4hours	]Day 3 dose end time+180min, Day 4[
Day 4	Day 4	[Day 4, Day 6]
Day 8 Pre-dose	Day 8 dose start time	[Day 7, Day 8 dose start time[
Day 8 15min Post-dose	Day 8 dose end time+15min	]Day 8 dose end time, Day 8 dose end time+30 min]
Day 8 60min Post-dose	Day 8 dose end time+60min	]Day 8 dose end time+30min, Day 8 dose end time+90min]
Day 8 2h Post-dose	Day 8 dose end time+2h	]Day 8 dose end time+90min, Day 10]
Day 15 Pre-dose	Day 15 dose start time	]Day 10, Day 15 dose start time[
Day 15 15min Post-dose	Day 15 dose end time+15min	]Day 15 dose end time, Day 15 dose end time+30 min]
Day 15 60min Post-dose	Day 15 dose end time+60min	]Day 15 dose end time+30min, Day 15 dose end time+90min]
Day 15 2h Post-dose	Day 15 dose end time+2h	]Day 15 dose end time+90min, Day 17]
Day 22 Pre-dose	Day 22 dose start time	]Day 17, Day 22 dose start time[
Day 22 15min Post-dose	Day 22 dose end time+15min	]Day 22 dose end time, Day 22 dose end time+30 min]
Day 22 60min Post-dose	Day 22 dose end time+60min	]Day 22 dose end time+30min, Day 22 dose end time+90min]
Day 22 2h Post-dose	Day 22 dose end time+2h	]Day 22 dose end time+90min, Day 26]
Day 33	Day 33	]Day 26 ; Day 33+7]
Day 54	Day 54	]Day 33+7 ; End of Study]

**Table 10: Time points for Urinalysis SAD**

Time point	Target	Interval for Analysis
Baseline	Day 1 dose start time	Most recent value prior to first dose
Day 2	Day 2	]Day 1 dose time, Day 3[
Day 3	Day 3	[Day 3, Day 4[
Day 4	Day 4	[Day 4, Day 7[
Day 8	Day 8	[Day 7, End of study]

**Table 11: Time points for Urinalysis MAD**

Time point	Target	Interval for Analysis
Baseline	Day 1 dose start time	Most recent value prior to first dose
Day 3 60min Post-dose	Day 3 dose end time+60min	]Day 1 dose end time, Day 3 dose end time+180min]
Day 3 4h Post-dose	Day 3 dose end time+4hours	]Day 3 dose end time+180min, Day 4[
Day 4	Day 4	[Day 4, Day 6]
Day 8 Pre-dose	Day 8 dose start time	[Day 7, Day 8 dose start time[
Day 8 60min Post-dose	Day 8 dose end time+60min	]Day 8 dose end time, Day 8 dose end time+90min]
Day 8 2h Post-dose	Day 8 dose end time+2h	]Day 8 dose end time+90min, Day 10]
Day 15 Pre-dose	Day 15 dose start time	]Day 10, Day 15 dose start time[
Day 15 60min Post-dose	Day 15 dose end time+60min	]Day 15 dose end time, Day 15 dose end time+90min]
Day 15 2h Post-dose	Day 15 dose end time+2h	]Day 15 dose end time+90min, Day 17]
Day 22 Pre-dose	Day 22 dose start time	]Day 17, Day 22 dose start time[
Day 22 60min Post-dose	Day 22 dose end time+60min	]Day 22 dose end time, Day 22 dose end time+90min]
Day 22 2h Post-dose	Day 22 dose end time+2h	]Day 22 dose end time+90min, Day 26]
Day 33	Day 33	]Day 26 ; Day 33+7]
Day 54	Day 54	]Day 33+7 ; End of Study]

